7.2 Handling of missing data and outliers

7.2.1 Missing data analysis methods

Missing data will only be imputed in the primary and sensitivity analyses for TEAR rate associated with ADA and other secondary variables that are mentioned in this document. Otherwise, missing data will not be imputed.

Subjects with missing data are either 1) subjects who completely miss post-baseline ADA data or 2) subjects who miss a portion of ADA data and for whom the TEAR positive or negative status cannot be determined. If a subject with partially missing ADA data already

meets the TEAR criteria, the subject is not considered to be a subject with missing data. To minimize any bias due to missing data, multiple imputation will be used to fill in missing values according to either of two TEAR criteria (binary response and continuous titer values) prior to deriving the TEAR and subsequently estimating the treatment difference and 90% confidence interval. Two imputation processes will be used for each of two TEAR criteria among the missing data. For baseline ADA negative subjects, post baseline binary response (positive or negative) will be imputed using logistic regression multiple imputation assuming missing not at random. For baseline positive subjects, missing titer values (continuous values) will be imputed with same treatment group non-missing subjects using pattern mixture model with the complete-case missing values (CCMV) method (Little 1993). In the case where there are sufficient number of retrieved dropouts, that is, if there are 6 retrieved dropout subjects in each treatment group, the missing values in that treatment group will be imputed by modelling the retrieved subgroup data. Retrieved dropout subjects are the subjects who discontinued assigned study treatment but still remain on the study and had their efficacy and safety measurements captured at the planned visits. If less than 6 retrieved dropout subjects in each treatment group, all non-missing subjects within same treatment group will be used to impute missing data by multiple imputation.

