For continuous-valued ADA titer, missing values prior to the last observed visit will be filled in with MCMC imputation to make the dataset monotone. Missing values after discontinuation will be imputed by regression imputation of the monotone missing dataset. If there are at least 6 retrieved dropouts in each treatment arm, then a pattern mixture model estimated from the retrieved values will be used for regression imputation of missing values. Otherwise, the complete case missing values method will be used. Missing values for the binary response variable will be imputed using a logistic regression multiple imputation model. A monotone missingness pattern will be created by taking a random draw from the binomial distribution with the same probability as the observed responses from the same treatment group at the same visit.

Pattern mixture models will be fit separately for ADA binary response and for ADA titer. Binary response will be imputed using a logistic regression imputation model, while ADA titer will use a continuous-valued regression. Independent variables in the regression will include the values at all prior visits. Each imputation will be repeated 30 times with a seed of 40872021 for ADA binary response and a seed of 41671703 for ADA titer. Code for the multiple imputation analyses is presented in Appendix 10.1.

If baseline value is missing, the missing baseline value will be imputed with six imputations based on binomial distribution using probability of no missing baseline values from same treatment group.

After imputation, the dataset containing the imputed visitwise TEAR positive or negative status binary response and the dataset containing the imputed ADA titer values will be merged by subject, visit, and imputation number. The Week 24 values will then be used to assign the status of TEAR positive or negative, as follows:

If the subject was ADA negative at baseline, then this subject will be considered TEAR positive if any post-baseline observed or imputed value was ADA positive; otherwise, the subject will be considered TEAR negative. The imputed titer values will not be considered in subjects who are ADA negative at baseline.

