10.1 Multiple imputation

Multiple imputation will be applied to fill in missing values for ADA binary response and for ADA titer.

For binary ADA response, if baseline ADA value is missing, the missing baseline value will be imputed (6 imputations) based on binomial distribution using probability of no missing baseline values from the same treatment group. After imputations, for subjects with negative baseline ADA (Section 10.1.1) missing post-baseline binary response (positive or negative) will be imputed using logistic regression multiple imputation. For subjects who are ADA positive at baseline (Section 10.1.2), missing post-baseline ADA continuous titer values will be imputed with same treatment group non-missing subjects using continuous MI model.

The steps are summarised below:

Section 10.1.1 describes the methodology for imputation of binary response, while Section 10.1.2 covers the imputation of continuous ADA titer, and Section 10.1.3 puts them together.

10.1.1 Multiple imputation for binary ADA response if baseline ADA is negative.

For purposes of these specifications, let $RESP_x$ represent the binary value (0 or 1) at Visit x , where x takes the values 0 (for Baseline) or 8–15. The seed that will be used in the multiple imputation of ADA binary response will be 40872021.

Missing values will be obtained from logistic regression imputation on the observed values of binary response. A fully conditional specification (FCS) method will be used to impute values from a non-monotone missing data pattern.

There are 3 steps to this process:

1. Create a dataset with one record per subject, containing all values of $RESP$ for all weeks (Baseline and Weeks 2–24 on one record); that is, each record would contain variables for $RESP_0$ and $RESP_8$ – $RESP_{15}$. The subject-level $RETRIEVED$ variable described in Section 8.7.2.1 can also be generated at this time for subjects who discontinued treatment, based on whether values after treatment discontinuation

- were retrieved (set retrieved=1) or remain missing (set retrieved=0).
2. Fill in missing values to make a monotone missing data pattern, by drawing random TEAR values from the binomial distribution based on the TEAR frequencies for the given visit within treatment group.

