 3. Run a pattern mixture model logistic regression to impute missing values to generate 30 imputed datasets. This will generate a single pooled dataset containing one observation per subject per imputation. All missing values will have been filled in for each subject.

Step 1.

The dataset for this imputation has to put the values for all weeks onto one record. That is, the dataset would have one record per subject, with 8 values for RESP0 and RESP8–RESP15. One way this can be accomplished is the following:

```
data analysis (keep=usubjid RESP0 RESP8-RESP14);
set indata;
by usubjid avisitn;
array R {9} RESP0 RESP8-RESP15;
retain RESP0 RESP8-RESP15;
if first.usubjid then do;
    resp0 = base;
    do visit = 8 to 15;
        R{visit} = .;
    end;
end;
do visit = 8 to 15;
    if avisit = visit then R{visit} = aval;
end;
if last.usubjid then output;
run;
```

STEP 2.

First a flag needs to be created to indicate which missing values need to be filled in. This is a visit-level variable for each subject. For explanatory purposes, this variable will be referred to as EMPTY_x for Visit x. For each visit where a subject has a missing value, use the logic below:

- If there is a non-missing value for any visit AFTER Visit x, then EMPTY_x=0;
- Else if there are no non-missing values for any of the remaining visits, then EMPTY_x=1;

Then all records with EMPTY_x=1 have to have their RESP_x value filled in with a randomly generated 0 or 1. One way this can be accomplished is the following:

```
/** step 2: Make missingness monotone */  
%global mylrate novrate;
```

```
%macro getrate(visnum);
```

```
    proc sort data=indata;  
        by trtgroup;  
    run;  
    ods exclude all;  
    proc freq data=indata;  
        by trtgroup;  
        table RESP&visnum;  
    ods output onewayfreqs=pct;  
    run;  
    ods exclude none;
```

```
    data binom;  
        set pct (where=(RESP&visnum=1));  
        probresp = percent/100;  
        if trtgroup="MYL-1601D" then call  
            symput("mylrate",probresp);  
        else if trtgroup="NOVOLOG" then call  
            symput("novrate",probresp);  
    run;
```

```
%mend getrate;
```

```
%macro fillin (visit);
```

```
    %getrate(&visit);
```

```
    data indata;  
        set indata;  
        if empty&visit=1 then do;  
            if trtgroup="MYL-1601D" then  
                RESP&visit=ranbin(86537043,1,&mylrate);  
            else if trtgroup="NOVOLOG" then  

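### Step 2 of the binary ADA imputation has its fill flag inverted: dropouts' remaining values through Visit 13 get random 0/1 draws, while the intermittent gaps it should fill are left

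*SAP*

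**What the plan says.** For subjects who are ADA negative at baseline, SAP Section 7.2.1 states that missing post-baseline binary results "will be imputed using logistic regression multiple imputation assuming missing not at random". Section 8.7.2.1 adds a preparatory step: "A monotone missingness pattern will be created by taking a random draw from the binomial distribution", at the observed rate for the same arm and visit. Section 10.1.1 gives Step 2 the same purpose: "Fill in missing values to make a monotone missing data pattern, by drawing random TEAR values from the binomial distribution".

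The operative rule in Step 2 sets a flag for each missing visit:

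- The first condition covers a gap that precedes an observed result: "If there is a non-missing value for any visit AFTER Visit x, then EMPTY_x=0". Such a gap is left alone.
- The second condition covers the tail after a subject's last result: "Else if there are no non-missing values for any of the remaining visits, then EMPTY_x=1". Such a visit is filled.

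Records with EMPTY_x=1 then have their "value filled in with a randomly generated 0 or 1". The code below the rule follows the prose: it draws only where the flag is 1, and it loops over Visits 8 to 13. Step 3 then runs monotone logistic imputation with an MNAR statement covering RESP8 to RESP15.

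Two related statements matter. The introduction to Section 10.1.1 names a different way of handling gaps: "A fully conditional specification (FCS) method will be used to impute values from a non-monotone missing data pattern". The endpoint rule in Section 8.7.2.1 is that "this subject will be considered TEAR positive if any post-baseline observed or imputed value was ADA positive".

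**The concern.** A pattern is monotone when nothing is observed after the first missing visit. To reach it, one fills gaps that have a later observed value and leaves the tail after the last observation. Step 2 leaves the gaps and fills the tail.

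This has two consequences for the primary endpoint. First, for a dropout, every missing visit up to Visit 13 is replaced by a draw that ignores the subject's own ADA history. Only Visit 15 (and the unsampled Visit 14) still reaches the MNAR model, where it is predicted partly from those draws. Since a single imputed positive makes the subject TEAR positive, each draw counts. Second, any remaining gap sends non-monotone data to the monotone statements in Step 3, so the primary imputation would have to be re-specified after the plan is final.

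Visit 14 makes the second consequence almost certain. The schedule in SAP Table 1 takes no immunogenicity sample at that visit, yet RESP14 is in the Step 3 models and the fill loop stops at Visit 13. Virtually every completer therefore has a gap immediately before an observed Visit 15.

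**Working it through.** **The rule against the plan's own text.** Sections 8.7.2.1 and 10.1.1 give monotonicity as the purpose of the binomial draw. Section 8.7.2.1 also describes the parallel titer procedure: values before the last observed visit are filled to reach monotonicity, and values after discontinuation go to the regression imputation. The binary flag does the opposite on both counts.

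**Applying the rule.** Order of sampled visits: V8, V9, V10, V11, V12, V13, V15. R is a random draw and a dot is still missing.

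| Pattern | As written | Conditions swapped |
|---|---|---|
| Dropout after V9 | 0 0 R R R R . | 0 0 . . . . . |
| Gap at V10 only | 0 0 . 0 0 0 0 (not monotone) | 0 0 R 0 0 0 0 |
| Gap at V9, dropout after V11 | 0 . 0 0 R R . (not monotone) | 0 R 0 0 . . . |
| No post-baseline data | R R R R R R . | . . . . . . . |

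Seven visits give 2^7 = 128 observed/missing patterns. Eight are already monotone, leaving 120. The written rule makes 0 of the 120 monotone; the swapped rule makes all 120 monotone. If Visit 14 stays in the model, a completer's pattern (V8 to V13 and V15 observed, V14 missing) is non-monotone under either rule.

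**Size for one dropout.** The documents give no persistence or dropout rates, so these are assumptions.

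- Take 20% ever positive over the seven visits. The onset chance per visit is h = 1 - 0.80^(1/7) = 0.031.
- Let s be the chance that a positive subject is still positive at the next visit. The visit rate is q_t = q_(t-1)·s + (1 - q_(t-1))·h, starting from q = 0.
- Consider a baseline-negative subject who is negative through V10 (Week 8) and missing afterwards.
- History-based chance of TEAR: 1 - (1 - h)^4 = 0.120.
- As written, independent draws: 1 - (1 - q_V11)(1 - q_V12)(1 - q_V13)(1 - h).
- The code reuses one fixed seed per arm at every visit. If the draws then repeat fully: 1 - (1 - max q)(1 - h).

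| Persistence s | q at V11, V12, V13 | Independent draws | Fully repeated draws |
|---|---|---|---|
| h (no serial correlation) | 0.031, 0.031, 0.031 | 0.120 | 0.062 |
| 0.5 | 0.056, 0.058, 0.058 | 0.189 | 0.088 |
| 0.8 | 0.088, 0.099, 0.108 | 0.290 | 0.136 |
| 1.0 | 0.120, 0.147, 0.174 | 0.400 | 0.200 |

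A Monte Carlo check of the independent-draw column (200,000 subjects) gave 0.121, 0.188, 0.291 and 0.398.

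**Size for the treatment difference.** Suppose 10% of one arm and 5% of the other are in this position. The shift is (0.10 - 0.05) × (as-written chance - 0.120).

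- Independent draws: 0, 0.35, 0.85 and 1.40 points.
- Repeated draws: -0.29, -0.16, +0.08 and +0.40 points.
- Equal missingness and equal rates: no shift.

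For scale, the SAP margin formula at a 20% reference rate gives 2.926 × sqrt(2 × 0.2 × 0.8 / 250) = 10.47 points, which reproduces the 10.5% in SAP Table 2.

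**Size for a whole arm.** A simulation used onset of 1% to 5% per visit, persistence of 0.7 or 0.9, 5% to 15% dropout at random, and independent draws. True TEAR among dropouts of about 7%, 19-20% and 30-31% was imputed as 11-14%, 29-36% and 43-52%. The whole-arm rate rose by about 0.1 to 3 points. With the conditions swapped, the dropouts' imputed rate stayed within about 1 point of the truth.

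**The case against.** The best defence is that the intent is plain from the main SAP text, and that the error is a swapped flag in an appendix of example code. That code cannot run literally in any case: for instance, a nine-element array is indexed 8 to 15, and the keep list omits RESP15. A programmer has to rewrite it and may notice the inversion. The appendix also names an FCS method, which could tolerate leftover gaps. Step 1 speaks of eight values per record, which matches baseline plus the seven sampled visits, so RESP14 may be a labelling slip. If Visit 14 stops Step 3 from running, the biased result cannot arise until someone repairs Visit 14 and misses the flag beside it. The programming flow chart in Section 10 is not visible in the text available and may show the intended flow. Finally, the direction is not fixed, the shift is small against the margin, and the observed-data, MYL-missing-as-positive and tipping-point analyses do not use this step.

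The points on size and direction stand, and they limit how serious this is. The rest does not remove the error. The flag rule is specification prose and not only sample code, and the code agrees with it. FCS would not undo the draws already placed in the dropouts' tails. RESP14 appears explicitly in the Step 3 models. A flow chart could show the intent but would leave contradictory text in place. The sensitivity analyses bound the risk without correcting the primary analysis.

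**Conclusion.** The specification is wrong as written, and that conclusion needs no assumption. The EMPTY_x conditions contradict the stated purpose of Step 2, the planned MNAR logistic imputation and the SAP's own titer procedure. The error reaches only subjects treated as ADA negative at baseline who are not already TEAR positive on observed data, and the draws fall only on visits after their last observed value.

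The numerical effect is conditional. Imputed TEAR among dropouts is too high if ADA status persists within subjects and the draws are independent across visits. With repeated draws it can be too low. Against a retrieved-dropout model the direction is unknown. A shift in the treatment difference requires missingness or rates to differ between arms; in the cases worked here it is at most 1.4 points. This should be corrected because it is the primary-endpoint imputation and the choice ought to be made before unblinding, not because it is likely to decide the trial by itself.

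**What to change.** 1. Swap the two conditions in Section 10.1.1 Step 2: EMPTY_x=1 only when Visit x is missing and a later visit is observed. Leave everything after the last observed visit to the Step 3 MNAR model.
2. Remove Visit 14 from the RESP and ADA arrays and models, and confirm that the pattern is monotone before Step 3.
3. Name one gap-filling method. Section 8.7.2.1 and Step 2 say a binomial draw; the introduction to Section 10.1.1 says FCS.
4. As a separate, smaller improvement, draw the gap fills within each of the 30 imputations. Step 2 currently runs once beforehand, so its draws are identical in all 30 datasets and add no between-imputation variance.

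The cost is an edit to SAP text and code before unblinding. No data collection or sample-size change is involved.

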7.2.2 Statistical Methodology for Primary Endpoints

The 90% confidence interval of treatment difference (MYL-1601D minus NovoLog®) in TEAR rate will be established using Wald confidence limit method. MYL-1601D TEAR rate is equivalent to that of NovoLog® during 24-week treatment period if 90% confidence interval of treatment difference in TEAR rate is within pre-specified margin defined in [Table 5](#). The pre-specified equivalent margin is dependent on the final rate of NovoLog® TEAR rate.

To minimize any bias due to missing data, multiple imputation will be used to fill in missing values for TEAR criteria (binary response and continuous titer values) prior to deriving the TEAR and subsequently estimating the treatment difference and 90% confidence interval.

The method of imputation for a subject will be dependent on the individual ADA result at baseline. For subjects with baseline ADA negative, post baseline binary response (positive or negative) will be imputed using logistic regression multiple imputation assuming missing not at random. For subjects with baseline positive, missing titer values (continuous values) will be imputed with same treatment group non-missing subjects using pattern mixture model with the complete-case missing values (CCMV) method ([Little 1993](#)).

In the case where there are sufficient number of retrieved dropouts, that is, if there are 6 retrieved dropout subjects in each treatment group, the missing values in that treatment group will be imputed by modelling the retrieved subgroup data. Retrieved dropout subjects are the subjects who discontinued assigned study treatment but still remain on the study and had their

efficacy and safety measurements captured at the planned visits. If less than 6 retrieved dropout subjects in each treatment group, all non-missing subjects within same treatment group will be used to impute missing data by multiple imputation.

If baseline value is missing, the missing baseline value will be imputed with single imputation based on binomial distribution using probability of no missing baseline values from same treatment group.

After imputation, the TEAR criteria will then be applied to each imputed dataset to obtain if a subject is TEAR positive or negative, and the treatment difference and 90% confidence interval will be estimated using Wald confidence limit method. The result will be combined over all imputations by SAS PROC MIANALYZE.

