2. Standard-of-care specifics includes assessment and documentation of the following - Training on self-management of diabetes, lifestyle modification measures (includes maintenance of appropriate body weight, following recommended physical activity, avoidance of smoking and following the recommended diet); and monitoring to prevent complications.
3. Serum pregnancy test for women of child bearing potential will be done during screening and randomization visits (V1 and V6). During subsequent visits urine pregnancy test will be done, any positive urine test needs to be confirmed with serum test. At the randomization visit, both urine and serum pregnancy tests will be done, subject can be enrolled only if the urine pregnancy test is negative until serum result is provided.
4. Non-severe hypoglycemic events (which are not consider as SAE) occurring after the EOT visit will not be recorded at the follow-up visit.
5. A routine urine dipstick test will be performed by the site. A microscopic urinalysis will be performed by the central lab if the dipstick test result is abnormal and the Investigator deems it clinically significant and requests further evaluation.
6. Rescue criterion is evaluated on V12/Week 16 based on HbA1c measurement at V11/Week 12. Sites are required to receive the V11/Week 12 results prior to V12/Week 16 subject visit to enable Investigator to take decision on future steps.
7. The 7-point SMBG profile recorded via glucometer and recorded by the subject in the diary, measurement will be performed by the subject at home on 3 days (of which 2 days are consecutive) in the week before the visit.
8. Prior to randomization, Investigator is required to re-confirm subject eligibility to the study based on the data collected during the screening period, including the labs values recorded during screening.
9. Immunogenicity samples: At Visits 1, 6, 8, 9, 10, 11, 12, 13 and 15. At each visit, five blood samples of 5 mL each (25 ml per visit) will be drawn for ADA and NAb.
10. In case the subject discontinues treatment early, the site should explain the importance of data collection and make every effort to retain the subject, perform the remaining visits, off study treatment, per the Schedule of Study Assessments, up to the completion of Week 28/Follow-up call. BMI is calculated at screening visit, randomization visit, week 12 and week 24.

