                RESP&visit=ranbin(48010557,1,&novrate);
```

```
end;  
run;
```

```
%mend fillin;
```

```
%macro monotone;  
  %do vis=8 %to 13;  
    %fillin(&vis);  
  %end;  
%mend monotone;
```

```
%monotone;
```

STEP 3.

Since SAS will not accept a binary variable as an independent variable in a logistic imputation model, continuous versions of the binary RESP variables. Both the continuous and categorical variables will be used during the regression. In the code below, the logistic regression code is different If there are <6 retrieved dropouts per group versus ≥ 6 .

```
/***/ setup: create numeric versions of binary variables  
***/  
data indata;  
set indata;  
array resps {7} resp0 resp8-resp14;  
array respns {7} respn0 respn8-RESPN14;  
do i=1 to 7;  
  respns{i} = resps{i};  
end;  
run;
```

```
/** step 3: Perform logistic regression imputation */  
  
/** Code to use if >=6 retrieved subjects per arm */  
proc mi data=indata nimpute=30 seed=40872021  
out=outdata;  
class resp8-resp15;  
var resp0n resp8 resp8n resp9 resp9n resp10 resp10n  
resp11  
    resp11n resp12 resp12n resp13 resp13n resp14 resp14n  
resp15;  
monotone logistic (resp8= resp0n) ;  
monotone logistic (resp9= resp0n resp8n) ;  
monotone logistic (resp10= resp0n resp8n resp9n) ;  
monotone logistic (resp11= resp0n resp8n resp9n resp10n)  
;  
monotone logistic (resp12= resp0n resp8n resp9n resp10n  
resp11n) ;  
monotone logistic (resp13=  
    resp0n resp8n resp9n resp10n resp11n resp12n) ;  
monotone logistic (resp14=  
    resp0n resp8n resp9n resp10n resp11n resp12n resp13n)  
;  
monotone logistic (resp15=  
    resp0n resp8n resp9n resp10n resp11n resp12n resp13n  
resp14n) ;  
mnar model (resp8-resp15 / modelobs=(retrieved=1));  
run;
```

```
/** Code to use if <6 retrieved subjects per arm */
proc mi data=indata nimpute=30 seed=40872021
out=outdata;
by trtgroup;
class resp8-resp15;
var resp0n resp8 resp8n resp9 resp9n resp10 resp10n
resp11
    resp11n resp12 resp12n resp13 resp13n resp14 resp14n
resp15;
monotone logistic (resp8= resp0n) ;
monotone logistic (resp9= resp0n resp8n) ;
monotone logistic (resp10= resp0n resp8n resp9n) ;
monotone logistic (resp11= resp0n resp8n resp9n resp10n)
;
monotone logistic (resp12= resp0n resp8n resp9n resp10n
resp11n) ;
monotone logistic (resp13=
    resp0n resp8n resp9n resp10n resp11n resp12n) ;
monotone logistic (resp14=
    resp0n resp8n resp9n resp10n resp11n resp12n resp13n)
;
monotone logistic (resp15=

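### The retrieved-dropout branch of the primary TEAR imputation starts at 6 subjects per arm, too few for its own all-earlier-visits model, and its example code omits the treatment split

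*SAP*

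**What the plan says.** Protocol 7.2.2 opens the branch "if there are 6 retrieved dropout subjects in each treatment group". SAP 7.2.1 repeats this, and SAP 8.7.2.1 words it as "If there are at least 6 retrieved dropouts in each treatment arm". Under the branch, "the missing values in that treatment group will be imputed by modelling the retrieved subgroup data". Below the trigger, the complete-case missing values (CCMV) method is used with same-arm subjects.

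Baseline ADA-negative subjects go to a logistic model for positive or negative status. Baseline-positive subjects go to a regression on titer. For both, "Independent variables in the regression will include the values at all prior visits" (SAP 8.7.2.1).

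In SAP 10.1.1 Step 3 the Visit 15 logistic model lists baseline and Visits 8 to 14. The donor statement when the trigger is met is "mnar model (resp8-resp15 / modelobs=(retrieved=1"; SAP 10.1.2 has the matching titer statement. Neither block has a BY statement or a treatment term, and nor does the titer MCMC step. Both below-trigger blocks have a BY statement.

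The sampling footnote to SAP Table 1 reads "Immunogenicity samples: At Visits 1, 6, 8, 9, 10, 11, 12, 13 and 15". Visit 14 is not among them.

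**The concern.** The trigger counts subjects without regard to the size of the model they must support, or to their split between two models. If it is met but a model cannot be fitted, someone must decide how to reduce the model, which arm may donate, or whether to abandon the branch. Those choices would be made with data in hand, and they feed the 90% confidence interval that decides equivalence. The secondary mixed models have a non-convergence rule (SAP 8.7.3); no such rule can be read for the primary imputation.

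The missing treatment split is a second matter. One donor model for both arms gives missing subjects in each arm the same behaviour, which tends to draw the TEAR difference toward zero, that is, toward equivalence.

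**Working it through.** **Inputs.** Trigger: 6 per arm (Protocol 7.2.2; SAP 7.2.1, 8.7.2.1). Post-baseline ADA samples: Visits 8, 9, 10, 11, 12, 13 and 15 (SAP Table 1). The trigger has no derivation to reproduce. The margins used in the pooling check do reproduce: (z0.95 + z0.90) × √(2p(1−p)/250) at p = 10% is (1.645 + 1.282) × √(0.18/250) = 7.85 points, against 7.9 in SAP Table 2.

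**Coefficients.** As coded, the Visit 15 logistic model has 8 predictors plus an intercept, so 9. Baseline is constant among baseline-negatives and Visit 14 is unsampled, which leaves 9 − 2 = 7. The titer model has an intercept, baseline and Visits 8 to 13: 1 + 1 + 6 = 8.

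| Visit imputed | 8 | 9 | 10 | 11 | 12 | 13 | 15 |
|---|---|---|---|---|---|---|---|
| Binary | 1 | 2 | 3 | 4 | 5 | 6 | 7 |
| Titer | 2 | 3 | 4 | 5 | 6 | 7 | 8 |

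**Donors at the trigger.** Same-arm: 6 < 7 and 6 < 8, so both Visit 15 models fall short however the 6 are split. Pooled: 12 < 7 + 8 = 15, so at least one does. Titer needs 9 donors to leave one residual degree of freedom. Seven binary donors are only a floor, since 7 points for 7 coefficients is a saturated fit. The early-visit models are small and may be fittable.

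**How many would be enough by count.** With n_pos ~ Binomial(N, q), require n_pos ≥ 9 and N − n_pos ≥ 7 in both arms with 90% probability. The documents give no baseline-positive share q, so it is varied:

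| q | 20% | 30% | 50% | 70% | 80% |
|---|---|---|---|---|---|
| N per arm | 69 | 45 | 26 | 37 | 56 |

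**Count is not enough.** Sets of baseline-negative donors were simulated with assumed visit positivity of 10, 30 or 50% and persistence of 0, 0.5 or 0.8, then checked for full rank and separation. The 7-coefficient model had no finite unique fit in 100% of sets with 6 donors, about 91 to 100% with 12, and about 2 to 100% with 30.

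**The CCMV model.** Visit 14 is ignored here. With 200 baseline-negative completers per arm, and two assumed rates of reverting to negative, the share of sets with no finite unique fit was:

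| Assumed TEAR rate | 5% | 10% | 20% | 30% |
|---|---|---|---|---|
| All earlier visits | 99.5–100% | 92.5–95% | 48–64% | 19–23.5% |
| Last value only | 45–51% | 10.5–23.5% | 1–1.5% | 0% |

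**Donor arm.** For titer, SAP 10.1 says missing values are imputed from observed subjects of the same arm, so the unsplit titer code conflicts with the text. For the binary model, "the missing values in that treatment group will be imputed by modelling the retrieved subgroup data" points to same-arm donors but does not say so.

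**Effect of pooling.** Simulated trials had 250 per arm, all baseline-negative, 10 or 20% dropout spread over the sampled visits, 6 or 12 retrieved donors per arm, a last-value model, and a true difference at the margin. The fill-in step matters. Its printed flag, "Else if there are no non-missing values for any of the remaining visits, then EMPTY_x=1", marks trailing gaps, which are then drawn "based on the TEAR frequencies for the given visit within treatment group", leaving little for the pooled model to do.

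| Fill-in step | Shift toward equivalence | One-sided error, pooled | One-sided error, same-arm |
|---|---|---|---|
| As printed | 0.05–0.26 points | 3.7–5.9% | 2.1–5.5% |
| Trailing gaps left open | 0.34–1.12 points | 1.5–5.1% | 0.3–4.5% |

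The nominal error is 5% and the Monte Carlo standard error about 0.3 points.

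**The case against.** Several defences have force.

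- **The lost flow chart.** SAP version 3.0 added a programming flow chart in Section 10, which is not shown. It may hold a fit-failure rule, so the claim is limited to the readable text. No readable passage, however, reconciles 6 donors with 7 or 8 coefficients.
- **Same-arm intent.** A count required in each arm makes little sense if donors are then pooled, and the titer text is explicit. This stands. A reader might infer from the code that pooling is planned; the documents do not support that. The code is offered as an example and should be reconciled with the text.
- **Visit 14.** As printed, every Step 3 model includes it, so the CCMV code has no scheduled complete case. A reader might infer that the fallback is unrunnable by design. The 7-element predictor array and the fill-in loop ending at Visit 13 suggest a slip.
- **Little consequence.** No attrition rate is assumed (Protocol 7.1), so the branch may never be used, and a short model matters only if it has values to impute. Analyses without imputation, with missing MYL-1601D subjects counted as positive, and by tipping point are planned (SAP 8.7.2.2, 8.7.2.3). These limit the damage but do not supply the primary estimate.

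**Conclusion.** The point stands as a rule that cannot be carried out at its own trigger. That conclusion rests only on the stated trigger, the stated predictors and the sampling schedule. Six is the minimum, and more retrieved dropouts ease the shortage, but how far depends on baseline ADA share and ADA persistence, which the documents do not give.

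The treatment split is a conflict between code and text for titer, and unstated though implied for the binary model. A reader might go on to conclude that the type I error is inflated. The simulations do not show that: the highest pooled figure, 5.9%, sits close to the same-arm maximum of 5.5%, and with trailing gaps left open the pooled error is at most 5.1%. What is at stake is pre-specification of the primary analysis. It should be fixed before unblinding.

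**What to change.** Before unblinding:

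- (a) Add a BY treatment statement to both retrieved-dropout blocks and to the titer MCMC step, and state that donors are same-arm.
- (b) Remove Visit 14 from every imputation model.
- (c) Cut the models to a few predictors, for example the last observed value, plus baseline titer in the titer model, and amend the predictor sentence in SAP 8.7.2.1.
- (d) For each model, use retrieved dropouts only if that model is estimable in both arms: full rank, no separation, and at least one residual degree of freedom for titer. Otherwise use same-arm CCMV with the same reduced predictors in both arms. Deciding arm by arm would put the two arms under different missing-data assumptions.
- (e) If the binary model is still separated, use a pre-specified same-arm draw that carries parameter uncertainty, such as a Beta draw of the visit rate, or a penalised or augmented logistic fit. This is needed because the reduced model can itself fail, as the CCMV table shows at low TEAR rates.

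If the flow chart already covers any of this, bring the text and code into line with it.

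The cost is text and code in SAP 7.2.1, 8.7.2.1 and 10.1 and matching wording in Protocol 7.2.2. Protocol Section 7 calls for an amendment if the change counts as major. No new data are needed. The price is that CCMV is used more often, so post-discontinuation data carry less weight, and a smaller model uses less of each subject's history.
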